
 • To assess the effect of the investigational regimens on anti-HBs • To assess the effect of VIR-3434 and TDF with or without VIR-2218, or VIR-2218 and PEG-IFNα on HBsAg • To assess the effect of VIR-3434 and TDF with or without VIR-2218, or VIR-2218 and PEG-IFNα on HBV DNA • To assess the effect of VIR-3434 and TDF with or without VIR-2218, or VIR-2218 and PEG-IFNα on HBeAg and anti-HBe • To assess the immunogenicity of VIR-3434 • To assess the effect of VIR-3434 and TDF with or without VIR-2218, or VIR-2218 and PEG-IFNα on ALT levels 	
 3. Proportion of participants with serum HBsAg \leq 10 IU/mL at 24 weeks post-end of treatment 4. Serum HBsAg levels and change from baseline across timepoints in the study 5. Serum HBsAg level at nadir during the study 6. Time to achieve nadir of serum HBsAg during the study 7. Time to achieve serum HBsAg loss (< 0.05 IU/mL) 8. Proportion of participants with HBsAg loss and anti-HBs seroconversion at end of treatment and at 24 weeks post-end of treatment 9. Proportion of participants achieving sustained suppression of HBV DNA ($<$ LLOQ) with HBsAg loss (< 0.05 IU/mL) after discontinuation of all treatment 
 a. at 24 weeks b. at the F48 Follow-Up visit 10. Proportion of participants achieving HBsAg loss (< 0.05 IU/mL) 
 a. at end of treatment b. at 24 weeks post-end of treatment 11. Proportion of participants achieving sustained suppression of HBV DNA ($<$ LLOQ) after discontinuation of all treatment 
 a. at 24 weeks b. at the F48 Follow-Up visit 12. For HBeAg-positive participants: proportion of participants with HBeAg loss (undetectable HBeAg) and/or anti-HBe seroconversion 13. Incidence and titers of anti-drug antibodies (ADA; if applicable) to VIR-3434

Objectives	Endpoints
	14. Mean change in serum HBsAg level from baseline across timepoints in the study 15. Proportion of participants achieving HBV DNA < LLOQ across timepoints in the study 16. Proportion of participants achieving ALT \leq ULN across timepoints in the study

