For event/measurement occurring on or after Day 1, the study day will be calculated as:

$$\text{Study Day} = (\text{Date of event/measurement} - \text{Date of first study drug administration}) + 1.$$

End of treatment (EOT) date: EOT date is the date of the last dose of VIR-2218, VIR-3434 and PEG-IFNa.

EOT assessment: The earliest available assessment on or after EOT date.

EOT + 24 weeks assessment: The earliest available assessment on or after EOT + 161 days.

Treatment Period and Follow-Up Period: Treatment Period and Follow-Up Period are defined in the protocol.

Treatment-emergent (TE) Period: The TE Period is defined as the time period on or from the start of study intervention(s) until the last dose of VIR-2218 + 30 days, or VIR-3434 + 24 weeks, or PEG-IFN α + 30 days, or TDF/TD + 30 days, whichever is later. The TE Period will be used for safety analysis.

Post-TE Period: The Post-TE Period is defined as the time period after the TE Period through the end of Follow-Up Period.

Analysis windows: The analysis window rules for protocol-defined visits are provided in [Appendix 2](#).

Unscheduled visits: Unscheduled visit measurements will be included in the analysis as follows:

1. In planned visit windows as specified, the analysis window rules described in [Appendix 2](#), if applicable.
2. In the derivation of the baseline.
3. In the derivation of maximum and minimum values, or maximum and minimum change from baseline values during the Treatment Period and Follow-Up Period for efficacy analyses, or worst values/grades during the TE Period for safety analyses.
4. In individual participant data listings as appropriate.

Repeated observations: Measurements recorded at different time points are defined as repeated observations. If an assessment has planned repeated measurements, then statistical summaries will present all planned time points, as appropriate.

If there are multiple records at a single assessment date, regardless of whether scheduled or unscheduled visit, the latest record will be used for the analysis.

Missing data handling conventions:

- Missing data can occur due to study withdrawal or participants lost to follow-up before the completion of the study or due to intermittent missing values (i.e., data between two non-missing assessments).
- Missing data in the by-participant data listings will be presented as missing.

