4.4. Secondary Endpoints Analysis

4.4.1. Secondary Efficacy Endpoints

The analysis of the following secondary endpoints will be conducted based on the FAS, unless otherwise specified. The numbering in the table below is consistent with the numbering of the endpoints in [Table 1](#). HBeAg, anti-HBsAg, and anti-HBeAg values will be provided in a by-participant listing.

Secondary Endpoints	Analysis Methods

 2. Proportion of participants with serum HBsAg ≤ 10 IU/mL at the EOT 3. Proportion of participants with serum HBsAg ≤ 10 IU/mL at 24 weeks post-EOT 8. Proportion of participants with HBsAg loss with anti-HBs seroconversion at EOT and at 24 weeks post-EOT 10. Proportion of participants achieving HBsAg loss (< 0.05 IU/mL) 
 a. at EOT b. at 24 weeks post-EOT 	
The number and proportion of participants for each endpoint will be summarized at each visit by cohort, and the two-sided 95% Clopper-Pearson CI will be calculated for each cohort.

 4. Serum HBsAg levels and change from baseline across timepoints in the study 5. Serum HBsAg level at nadir during the study 14. Mean change in serum HBsAg level from baseline across timepoints in the study 	
The observed values and the absolute change from baseline values in both IU/mL and \log_{10} IU/mL of HBsAg
 
at each visit up to end of study (EOS)
 
at nadir during the study
 
will be summarized using descriptive statistics (n, mean, SD, median, Q1, Q3, min, max) by cohort.
 
In addition, the change from baseline in \log_{10} IU/mL at each visit will be plotted for each participant by cohort.
 
Absolute value in \log_{10} IU/mL at each visit will be plotted for each participant by cohort.
 
Mean change from baseline in \log_{10} IU/mL at each visit will be plotted for each cohort.

6. Time to achieve nadir of serum HBsAg during the study
 
7. Time to achieve serum HBsAg loss (< 0.05 IU/mL)
	
Time-to-nadir of serum HBsAg during the study period (up to EOS) will be summarized as a continuous variable by cohort.
 
Time-to-HBsAg loss will be summarized as a continuous variable by cohort.

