12. For HBeAg-positive participants: proportion of participants with HBeAg loss (undetectable HBeAg) and/or anti-HBe seroconversion	
The number and percentage of participants achieving
 
 • HBeAg loss (undetectable HBeAg) will be summarized at each visit up to EOS by cohort for each visit; and • Anti-HBe seroconversion • HBeAg loss (undetectable HBeAg) and anti-HBe seroconversion will be summarized at each follow-up visit by cohort up to EOS. The two-sided 95% Clopper-Pearson CI will also be calculated at each follow-up visit for each cohort. 
The percentage will be based on those participants who have HBeAg tested positive at baseline in the FAS.

15. Proportion of participants achieving HBV DNA < LLOQ across timepoints in the study	
The number and percentage of participants with
 
 • HBV DNA < LLOQ • ALT \leq ULN

16. Proportion of participants achieving ALT \leq ULN across timepoints in the study	
will be summarized at each visit by cohort. The two-sided 95% Clopper-Pearson CI will also be calculated across visits for each cohort.
 
In addition, the individual ALT (U/L) value at each visit will be plotted for each participant by cohort.

--	---

- The LLOQ for HBV DNA is 20 IU/mL.
- HBsAg loss is defined as HBsAg < 0.05 IU/mL.
- Anti-HBs seroconversion: Anti-HBs change from baseline negative to post-baseline positive. The quantitative results will be used. The definition of negative, indeterminate, and positive is < 8.50 mIU/mL, ≥ 8.50 mIU/mL and < 11.50 mIU/mL, and ≥ 11.50 mIU/mL, respectively. If a result is “indeterminate”, a further assessment or judgement will be performed to determine positive or negative.
- HBeAg-positive participants: the qualitative results at Screening will be used to determine if a participant is HBeAg-positive. In case a participant has a missing qualitative result in screening, the most recent non-missing qualitative result before the first dose of the study intervention will be used. If the qualitative result is not available, then the most recent non-missing quantitative value before the first dose of the study intervention will be used.
- Undetectable HBeAg/HBeAg loss: HBeAg < 0.06 IU/mL.

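### STRIVE endpoint 8 has no rule to separate VIR-3434 from host anti-HBs if the assay detects the drug; the exposure is mainly at EOT

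*SAP*

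**What the plan says.** The SAP supplied is for STRIVE; the protocol supplied is for the sister sub-protocol THRIVE.

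STRIVE secondary endpoint 8 (SAP 1.1, Table 1) is "Proportion of participants with HBsAg loss and anti-HBs seroconversion at end of treatment and at 24 weeks post-end of treatment". SAP 4.4.1 gives the scoring rule: "Anti-HBs seroconversion: Anti-HBs change from baseline negative to post-baseline positive. The quantitative results will be used". Negative is below 8.50 mIU/mL, positive is 11.50 mIU/mL or more, and the band between is indeterminate. Only for that band does the SAP say that "a further assessment or judgement will be performed to determine positive or negative".

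The timepoints are set in SAP 4.1:
- The anchor is tied to dosing: "EOT date is the date of the last dose of VIR-2218, VIR-3434 and PEG-IFNa".
- The sample scored at that anchor may be taken on the same day, since the rule reads "EOT assessment: The earliest available assessment on or after EOT date".
- The later timepoint opens one week short of 24 weeks: "EOT + 24 weeks assessment: The earliest available assessment on or after EOT + 161 days".

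For the group of endpoints that includes 8, the method is "The number and proportion of participants for each endpoint will be summarized at each visit by cohort", with Clopper-Pearson intervals. The EOT version is also on the list for Interim Analysis 2 (SAP 4.9.4.5.2), which SAP 4.10.1 merges with Interim Analysis 1. SAP 4.4.4 to 4.4.6 plan no sensitivity, supplementary or subgroup analyses for secondary endpoints.

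SAP Table 3 gives VIR-3434 in all five cohorts. Protocol 2.2 and 2.3.1 describe it as a human IgG monoclonal antibody against HBsAg. Protocol 4.3.1 gives a half-life of about 25 days in healthy volunteers, with drug measurable up to 24 weeks after one subcutaneous dose.

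**The concern.** By its target, VIR-3434 is an anti-HBs antibody. Endpoint 8 reads anti-HBs when the last dose is given, with earlier doses still in the circulation, and nothing in the rule asks how much drug is in the sample. If the assay responds to the drug, a baseline-negative participant who has lost HBsAg could be scored as seroconverted without making any antibody. At EOT, endpoint 8 would then move towards endpoint 10a (HBsAg loss alone) and say little about host immunity, which is its purpose. With VIR-3434 in every cohort, no drug-free cohort would reveal this.

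**Working it through.** **Planning rates.** No size or power is attached to endpoint 8. SAP Table 6 is used only for its HBsAg-loss rates. Its powers at 25% reproduce with an exact binomial test against 2%: 75.6% for n = 10 (at least 2 responders) and 76.4% for n = 15 (at least 3).

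**Drug level: inputs.** All are from Protocol 4.3.1: half-life 25 days; 13 doses of 300 mg every 4 weeks, projected to AUC 5,148 day·µg/mL and Cmax 50 µg/mL; 3,000 mg IV, AUC 11,842. The model is one compartment with superposition, k = ln 2 / 25 = 0.02773 per day. The scale S is the concentration that one dose would add if absorbed at once.

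- AUC anchor: 5,148 / 13 = 396 per dose; S = 396 × 0.02773 = 10.98.
- Peak anchor: accumulation over 13 doses = 1.852; S = 50 / 1.852 = 27.0 (32.9 if absorption peaks at 10 days).
- IV anchor (dose-proportional, full bioavailability assumed): 11,842 / 10 = 1,184.2; S = 32.8.

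The anchors do not agree with one another in this simple model, so they are carried as a range.

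**Formulas.** Pre-dose at dose 12 (Week 44): C = S × Σ exp(−28jk), j = 1 to 11. At 25 days the sum is 0.852, so the AUC anchor gives 10.98 × 0.852 = 9.4. Day 161 after dose 12: C = S × exp(−161k) × Σ exp(−28jk), j = 0 to 11, which is 10.98 × 0.01152 × 1.852 = 0.23. Protocol 4.3.1 expects faster elimination when HBsAg is present, so half-lives of 5 to 15 days were also run with S unchanged. That range is an assumption.

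| Anchor, absorption | EOT pre-dose, 25 d | 15 d | 5 d | Day 161, 25 d | 15 d |
|---|---|---|---|---|---|
| AUC, instant | 9.4 | 4.1 | 0.23 | 0.23 | 0.009 |
| AUC, slow (0.1/day) | 12.0 | 6.4 | 1.2 | 0.32 | 0.017 |
| Peak, instant | 23.0 | 10.2 | 0.57 | 0.58 | 0.022 |
| Peak, Tmax 10 d | 31.6 | 15.3 | 1.5 | 0.79 | 0.033 |
| IV, instant | 28.0 | 12.4 | 0.69 | 0.70 | 0.027 |
| IV, slow (0.1/day) | 35.8 | 19.1 | 3.7 | 0.97 | 0.049 |

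Values are in µg/mL. At EOT the range is about 9 to 36 at 25 days. At 5 to 15 days it is about 0.2 to 15 under the AUC (instant) and peak anchors, and up to about 19 under the IV anchor with slow absorption. The upper ends move with the assumed absorption and are not hard bounds. The figures fit cohorts 1a and 4a; 5a (13 doses) is the same to three digits. Cohort 3a is lower: at 25 days with instant absorption, 2.9 to 8.8 (every 8 weeks) or 1.2 to 3.5 (every 12 weeks). Cohort 2a cannot be computed, because its dose is given only as up to 300 mg. Pre-dose sampling is the THRIVE rule (Protocol Table 8, footnote a), assumed here for STRIVE.

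**Assay response needed.** Drug alone reads 11.50 mIU/mL at 11.5 / C, in IU/mg (the same as mIU/µg):
- EOT, 25 days: 11.5 / 35.8 = 0.32 to 11.5 / 9.36 = 1.2.
- EOT, 5 to 15 days: 11.5 / 19.1 = 0.60 to 11.5 / 0.231 = 50.
- Day 161, 25 days: 11.5 / 0.97 = 12 to 11.5 / 0.234 = 49.
- Day 161, 15 days: at least 11.5 / 0.0494 = 233.

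The true value is not in the documents.

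**Effect on the proportion.** Suppose that every participant with HBsAg loss is baseline-negative and the assay reads drug. Endpoint 8 then equals the HBsAg-loss rate, whatever the host response.
- n = 15 at 25%: 3.75, about 4. Reported 4/15 = 26.7% (95% CI 7.8 to 55.1). If two truly seroconvert, the host figure is 13.3% (1.7 to 40.5); if none, 0% (0 to 21.8).
- n = 10 at 40%: 4/10 = 40% (12.2 to 73.8), against 0% (0 to 30.8) if none.
- n = 15 at 40%: 6/15 = 40% (16.3 to 67.7), against 0% (0 to 21.8) if none.

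**The case against.** The strongest objection is that the premise lies outside the documents. Whether the assay detects VIR-3434 is a laboratory fact, and the Master Protocol, STRIVE protocol and Laboratory Manual, any of which might state it, were not supplied. If the assay does not respond to the drug, there is no bias. This stands, and it limits the point to a gap in the rule.

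Much is also mitigated already. HBsAg loss is still required, and a participant positive at baseline cannot qualify. The primary and sustained-suppression endpoints do not use anti-HBs. SAP 2 calls the study exploratory, with no hypothesis testing. The SAP says that "HBeAg, anti-HBsAg, and anti-HBeAg values will be provided in a by-participant listing", and SAP 4.8.1.2 lists VIR-3434 concentrations. All of this stands, but listings do not change a tabulated proportion labelled seroconversion.

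The instruction to summarize at each visit can be read two ways. If it means every visit, late follow-up offers an almost drug-free reading: at 25 days with instant absorption, the AUC and peak anchors give about 0.02 to 0.05 µg/mL at 36 weeks after the last dose. If it means only the two named timepoints, that help is absent. Early termination will thin late data in either case.

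A reader might infer that the EOT result should be withdrawn until the assay question is settled. The documents do not support that: interference is unproven, and a label with a split keeps the prespecified result.

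**Conclusion.** The concern holds as a conditional one. As written, the rule cannot separate drug from host antibody if the assay detects VIR-3434, and EOT is where drug is high enough for this to matter most. At 24 weeks post-EOT drug is at least about 35 times lower, so interference there is possible but needs a far stronger assay response.

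The overstatement ranges from zero to the full HBsAg-loss rate among baseline-negative participants. The 26.7 and 40 points are illustrations at the SAP's planning rates; neither is a forecast, and 26.7 is not a ceiling.

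Two stronger readings are tempting. One is that the assay does detect the drug, so the EOT figure is wrong; the documents neither show nor exclude this. The other is that the 24-week figure is equally affected; the projected levels do not support it.

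The drug levels rest on healthy-volunteer projections, a one-compartment model, assumed absorption, an assumed 5 to 15 day range for faster clearance, and pre-dose sampling carried over from THRIVE. Severity is minor.

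**What to change.** 1. State in the SAP, from assay documentation, whether the anti-HBs assay detects VIR-3434 and, if so, the drug concentration that reads 11.50 mIU/mL. If it does not detect the drug, nothing else need change.
2. If it does, or if this is unknown, keep endpoint 8 as prespecified (FAS, missing equals failure). Label the EOT figure and any other on-treatment figure, including those in the combined first and second interim analysis, as anti-HBs positivity that may include drug and is not evidence of host seroconversion.
3. At EOT and at 24 weeks post-EOT, within the same denominator, split responders by same-visit VIR-3434, naming the drug assay (free or total) and its LLOQ. The three lines are: below the concentration that could read 11.50 mIU/mL (or below quantitation if that concentration is unknown); at or above it; and no usable drug result. They sum to the reported count.
4. If THRIVE uses the same Master Protocol endpoint 8, as Protocol Section 3 suggests, carry the rule into its SAP, which was not supplied.

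The cost is one SAP statement and a few table lines from values that STRIVE already lists. The drug-free count may be small, most of all if below quantitation has to serve as the cut. STRIVE's PK visit schedule was not supplied, so the number without a usable drug result cannot be judged here.

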4.4.2. Secondary Endpoints for Safety

The analysis of the following secondary endpoints for safety will be conducted based on the Safety Analysis Set, unless otherwise specified:

Secondary Endpoints	Analysis Methods
1. Proportion of participants with treatment-emergent adverse events (TEAEs) and serious adverse events (SAEs)	
The number and percentage of participants with
 
 • TEAEs • SAEs 
will be summarized by cohort.

For a complete description of safety analyses for adverse events, please see [Section 4.7.3](#).

All safety analyses, including but not limited to Exposure, Study Intervention Compliance, Safety Laboratory tests, Event of Clinical Interest (ECI), Vital Signs, please see [Section 4.7](#).

4.4.3. Secondary Endpoints for Immunogenicity

The analysis of the following immunogenicity secondary endpoints will be conducted based on the Immunogenicity Analysis Set, unless otherwise specified:

Secondary Endpoints	Analysis Methods
13. Incidence and titers of ADA (if applicable) to VIR-3434	For a complete description of Immunogenicity Analysis, please see Section 4.8.2 .

4.4.4. Sensitivity Analysis

Not applicable.

4.4.5. Supplementary Analysis

Not applicable.

4.4.6. Subgroup Analysis

Not applicable.

4.5. Exploratory Endpoints Analysis

4.5.1. Exploratory Efficacy Analysis

The analyses of the following exploratory efficacy endpoints will be conducted based on the FAS, unless otherwise specified. The numbering in the table below is consistent with the numbering of the endpoints in [Table 1](#). HBV RNA and HBcrAg values will be provided in a by-participant listing.

[figure not shown]
Exploratory Endpoints	Analysis Methods
1. Additional viral parameters associated with HBV and/or study intervention(s), including but not limited to HBV RNA and HBcrAg	
The observed values and the absolute change from baseline values at each visit up to End of Follow-up will be summarized using descriptive statistics (n, mean, SD, median, Q1, Q3, min, max) by cohort for the following HBV viral parameters:
 
 • HBV RNA in \log_{10} U/mL • HBcrAg in \log_{10} U/mL

Exploratory Endpoints	Analysis Methods
2. CCI	CCI
3. CCI	CCI
4. Emergence of viral resistance to study intervention(s)	Not covered by this SAP, will be analyzed separately.
7. For HBeAg-positive participants: time to achieve HBeAg loss (undetectable HBeAg) and/or anti-HBe seroconversion	Time to HBeAg loss and/or anti-HBe seroconversion will be summarized as a continuous variable. Participants with HBeAg loss with or without anti-HBe seroconversion will be listed.
8. Proportion of participants meeting criteria for NRTI discontinuation or retreatment in the study	The number and percentage of participants who meet NRTI discontinuation criteria NRTI retreatment criteria will be summarized by cohort. A by-participant listing will be provided for participants who met NRTI discontinuation criteria and retreatment criteria.
9. HBV DNA levels and change from baseline across timepoints in the study 10. Nadir and maximum change of HBV DNA level from baseline in the study	The observed values and the absolute change from baseline values of HBV DNA in both log IU/mL and IU/mL: a. at each visit b. at nadir up to EOS, will be summarized using descriptive statistics (n, mean, SD, median, Q1, Q3, min, max) by cohort. In addition, the change from baseline in \log_{10} IU/mL and absolute value in \log_{10} IU/mL at

Exploratory Endpoints	Analysis Methods
	each visit will be plotted for each participant by cohort.
14. Proportion of participants with virological relapse (defined as either (1) an increase of $\geq 1 \log_{10}$ HBV DNA IU/mL above nadir for at least 2 consecutive visits OR (2) quantifiable HBV DNA of $\geq 1 \log_{10}$ IU/mL above LLOQ for at least 2 consecutive visits after being < LLOQ)	The number and percentage of participants with virological relapse will be summarized during the study.

CCI

CCI

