1.2.3. Intervention Groups and Duration

There are 5 cohorts planned in this sub-study.

Table 3: Intervention Groups

Cohort	Study Drug	Dose	Route	Number of Doses	Frequency of Dosing
1a	VIR-3434	300 mg	SC	12	Every 4 weeks
	TDF	300 mg ^b	Oral	\geq 308 ^c	Every day
2a	VIR-3434	Up to 300 mg ^a	SC	12	Every 4 weeks
	TDF	300 mg ^b	Oral	\geq 308 ^c	Every day
3a	VIR-3434	300 mg	SC	4-6 ^d	Every 8-12 weeks ^d
	TDF	300 mg ^b	Oral	\geq 252 ^c	Every day
4a	VIR-3434	300 mg	SC	12	Every 4 weeks
	VIR-2218	200 mg	SC	12	Every 4 weeks
	TDF	300 mg ^b	Oral	\geq 308 ^c	Every day
5a	VIR-3434	300 mg	SC	13	Every 4 weeks
	VIR-2218	200 mg	SC	13	Every 4 weeks
	PEG-IFN α	180 mcg	SC	48	Every week
	TDF	300 mg ^b	Oral	\geq 336 ^c	Every day

^a The dose of VIR-3434 will be determined before participants are enrolled in the cohort.

^b Tenofovir disoproxil fumarate dose (TDF) will be 300 mg as approved by the FDA. Supply outside the United States may be Tenofovir disoproxil (TD) 245 mg.

^c The minimum number of doses received by participant. Participants will continue receiving additional doses of TDF until they qualify for NRTI discontinuation.

^d The dosing regimen will be finalized before participants are enrolled in the cohort.

The total duration in the study for participants will be up to 100 weeks in cohorts 1a, 2a, and Cohort 4a, 92-96 weeks for Cohort 3a, and 104 weeks for Cohort 5a. This includes a Screening Period (up to 56 days or 8 weeks), Treatment Period (44 weeks for cohorts 1a and 2a, 36 or

40 weeks for Cohort 3a, 44 weeks for Cohort 4a, and 48 weeks for Cohort 5a) and a Follow-Up Period (up to 48 weeks) for all cohorts.

Once participants complete the Treatment Period per their respective cohort, they will enter the Follow-Up Period. Participants will discontinue the NRTI at the F1 or F12 visit in the Follow-Up Period if they meet the criteria to discontinue NRTI ([Section 1.2.4](#)) based on the data available. Additional study visits are required for participants who discontinue NRTI in the Follow-Up Period as indicated in the SOA in the study protocol. Participants who discontinue NRTI at F1 visit will be required to return to the site for additional visits at F2, F6, F10, F28, F32, F40, and F44. Participants who discontinue NRTI at F12 visit will be required to return to the site for additional visits at F14, F18, F22, F28, F32, F40, and F44.

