- Anti-HBe seroconversion: Anti-HBe changes from baseline negative to post-baseline positive. Anti-HBe qualitative data at Screening will be used for baseline assessment. Anti-HBe qualitative data collected during the Follow-Up Period will be used for post-baseline assessment.
- Nadir of HBsAg (or HBV DNA): Nadir is defined as the lowest HBsAg (or HBV DNA) value among all scheduled and unscheduled post-baseline HBsAg (or HBV DNA) values.

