4.9.3.5.2. Secondary Endpoints Analysis

For IA1, the secondary endpoints analysis will be performed as described in [Section 4.4.1](#), including the endpoints below:

- Serum HBsAg levels and change from baseline across timepoints in the study
- Serum HBsAg level at nadir during the study
- Time to achieve serum HBsAg loss
- For HBeAg-positive participants: proportion of participants with HBeAg loss (undetectable HBeAg) and/or anti-HBe seroconversion
- Mean change in serum HBsAg level from baseline across timepoints in the study
- Proportion of participants achieving HBV DNA < LLOQ across timepoints in the study
- Incidence and titers of ADA (if applicable) to VIR-3434
- Proportion of participants achieving ALT \leq ULN across timepoints in the study

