Analysis Window	< D1 dose time			≥D1 dose time, +28		±28		-28, +42			±42			-42, +14		-14, EOT Date	
CLDQ-HBV, WPAI:GH																	

Table 11: Analysis Windows for Safety, Efficacy, and other Assessments: Follow-Up Period for Participants Who Never Discontinue NRTI during Follow-Up Period

Study Stage	Follow-Up Period								
	Follow up Visit	F1	F4	F8	F12	F16	F20	F24	F36
Visit Day ± Visit Window	D8 ±2	D29 ±7	D57 ±7	D85 ±7	D113 ±7	D141 ±7	D169 ±7	D253 ±7	D337 ±7
Analysis Visit	FU Week 1	FU Week 4	FU Week 8	FU Week 12	FU Week 16	FU Week 20	FU Week 24	FU Week 36	FU Week 48/EOFU
Analysis Window	EOT DATE , +7	±14	±14	±14	±14	±14	-14, +42	±42	-42, +14
HBV DNA quantification, HBsAg quantitative, Liver function tests, Serum chemistry, Hematology, Coagulation parameters, Anti-HBs quantitative, HBeAg quantitative, Anti-HBe qualitative.									
Analysis Visit	FU Week 1	FU Week 4		FU Week 12			FU Week 24		FU Week 48/EOFU
Analysis Window	EOT DATE , +7	-14, +28		-28, +42			-42, +84		-84, +14
HBcrAg, HBV RNA.									
Analysis Visit	FU Week 1			FU Week 12			FU Week 24		FU Week 48/EOFU
Analysis Window	EOT DATE , +35			±42			-42, +84		-84, +14
CLDQ-HBV, WPAI:GH.									

Table 12: Analysis Windows for Safety, Efficacy, and other Assessments: Follow-Up Period for Participants Who Discontinue NRTI at F1

Study Stage	Follow-Up Period															
	Follow up Visit	F1	F2	F4	F6	F8	F10	F12	F16	F20	F24	F28	F32	F36	F40	F44

Visit Day ± Visit Window	D8 ±2	D15 ±2	D29 ±7	D43 ±7	D57 ±7	D71 ±7	D85 ±7	D113 ±7	D141 ±7	D169 ±7	D197 ±7	D225 ±7	D253 ±7	D281 ±7	D309 ±7	D337 ±7
Analysis Visit	FU Week 1	FU Week 2	FU Week 4	FU Week 6	FU Week 8	FU Week 10	FU Week 12	FU Week 16	FU Week 20	FU Week 24	FU Week 28	FU Week 32	FU Week 36	FU Week 40	FU Week 44	FU Week 48/EOFU
Analysis Window	EOT DATE ,+2	-5, +7	±7	±7	±7	±7	-7, +14	±14	±14	±14	±14	±14	±14	±14	±14	±14
HBV DNA quantification, HBsAg quantitative, Liver function tests, Serum chemistry, Hematology, Coagulation parameters, Anti-HBs quantitative, HBeAg quantitative, Anti-HBe qualitative.																
Analysis Visit	FU Week 1		FU Week 4				FU Week 12			FU Week 24						FU Week 48/EOFU
Analysis Window	EOT DATE ,+7		-14, +28				-28, +42			-42, +84						-84, +14
HBcrAg, HBV RNA.																
Analysis Visit	FU Week 1						FU Week 12			FU Week 24						FU Week 48/EOFU
Analysis Window	EOT DATE ,+35						±42			-42, +84						-84, +14
CLDQ-HBV, WPAI:GH.																

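### For STRIVE treatment completers, time to anti-HBe seroconversion dates lasting on-treatment events to about the first follow-up visit, so it reflects the cohort's treatment length

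*SAP*

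**What the plan says.** This point concerns the SAP supplied, which is for the STRIVE sub-study.

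- **Endpoint.** Section 4.5.1, exploratory endpoint 7, for HBeAg-positive participants: "Time to HBeAg loss and/or anti-HBe seroconversion will be summarized as a continuous variable". No time origin, censoring rule or detection rule is attached.
- **Source of the anti-HBe data.** Among the definitions in Section 4.4.1: "Anti-HBe qualitative data at Screening will be used for baseline assessment", and then "Anti-HBe qualitative data collected during the Follow-Up Period will be used for post-baseline assessment".
- **Windows.** In Appendix 2, the follow-up tables (11 to 13) include anti-HBe: "Coagulation parameters, Anti-HBs quantitative, HBeAg quantitative, Anti-HBe qualitative". The treatment-period tables (7 to 10) include quantitative HBeAg, at Week 4 and every 4 weeks after that, but no anti-HBe.
- **Secondary endpoint 12.** Section 4.4.1 respects this limit. HBeAg loss is summarized at all visits, and seroconversion only at follow-up visits.
- **Treatment length.** Section 1.2.3: "Treatment Period (44 weeks for cohorts 1a and 2a, 36 or" and, continuing, "40 weeks for Cohort 3a, 44 weeks for Cohort 4a, and 48 weeks for Cohort 5a". Footnote d to Table 3 says the Cohort 3a regimen is fixed before anyone is enrolled in that cohort.
- **EOT.** Section 4.1: "EOT date is the date of the last dose of VIR-2218, VIR-3434 and PEG-IFNa". The follow-up windows open from that date.

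**The concern.** Endpoint 12 was fitted to the data that exist; endpoint 7 was not. A participant who turns anti-HBe positive during treatment has no usable sample showing it until follow-up starts. The recorded time is then the date of the first follow-up sample, which is treatment length plus about one week.

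HBeAg loss, the other half of the endpoint, is measured every 4 weeks on treatment. One line of the plan therefore puts two different clocks together without saying which is reported.

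Section 4.1 has efficacy endpoints summarized for each cohort, and treatment lengths differ by cohort. A table of mean or median time to seroconversion could then show cohorts apart for reasons of schedule alone. A censoring rule for participants without the event would not cure this, because the difficulty lies in the dates of those who have it.

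**Working it through.** **Inputs.** Screening is 8 weeks, follow-up is 48 weeks, and treatment lengths are as quoted (Section 1.2.3). Planned EOT visit days are 309 for 1a/2a and 4a, 253 or 281 for 3a, and 337 for 5a (Tables 7 to 10). F1 is follow-up Day 8 ±2 (Tables 11 to 13), that is, EOT + 7 days.

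**The plan's own figure first.** Total duration = screening + treatment + follow-up:

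- 1a, 2a, 4a: 8 + 44 + 48 = 100 weeks
- 3a: 8 + 36 + 48 = 92, or 8 + 40 + 48 = 96 weeks
- 5a: 8 + 48 + 48 = 104 weeks

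All agree with Section 1.2.3, so the treatment lengths are read correctly. The SAP gives no figure for the earliest seroconversion time.

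**First scheduled usable post-baseline anti-HBe, treatment completers.** F1 day = EOT day + 7. Weeks since Day 1 = (F1 day − 1)/7. Counting from Day 1 is an assumption, since endpoint 7 states no origin; it follows the study-day definition in Section 4.1.

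| Cohort | EOT day | F1 day | Week |
|---|---|---|---|
| 3a, every 12 weeks | 253 | 260 | 259/7 = 37 |
| 3a, every 8 weeks | 281 | 288 | 287/7 = 41 |
| 1a, 2a, 4a | 309 | 316 | 315/7 = 45 |
| 5a | 337 | 344 | 343/7 = 49 |

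Visit windows of ±2 days at EOT and ±2 days at F1 shift each value by at most 4/7, about 0.6 week.

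**Gaps due to schedule alone.** 5a against 4a: 49 − 45 = 4 weeks. 5a against 3a: 49 − 41 = 8 or 49 − 37 = 12 weeks, depending on which single regimen 3a uses.

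**One case.** A lasting seroconversion at Week 12 in Cohort 4a is recorded at Week 45, which is 45 − 12 = 33 weeks late.

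**Illustration.** Assume that true seroconversion times are uniform over Weeks 4 to 36 in every cohort (true median Week 20), and that everyone completes treatment, attends F1 and is still positive there. The recorded medians are then 37, 41, 45 and 49 weeks with a standard deviation of 0. All the difference between cohorts is treatment length. The uniform distribution is chosen only to show the mechanism; the documents give no seroconversion rate or timing.

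**The case against.** Much can be said on the other side, and most of it limits the point.

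- **No one can be dated before Week 37.** A reader might infer this, but the SAP does not support it. EOT is the last-dose date and the follow-up windows open from it, so a participant who stops early can have follow-up anti-HBe sooner. Someone stopping at Week 12 could have F1 at about Week 13. The SAP provides for early stoppers in Sections 3 and 4.3.2. The STRIVE protocol, which would give their visit schedule, is not among the documents.
- **Every seroconversion date is wrong.** This too goes beyond the text. An event that first arises in follow-up is dated to within the spacing of follow-up visits.
- **The whole endpoint is affected.** This depends on how the and/or is read. If either event counts, a participant with on-treatment HBeAg loss takes the date of that loss, and the result is driven mainly by HBeAg loss. The artefact falls on the stand-alone seroconversion time and on the version requiring both events.
- **The interim analyses are a second error.** The IA1 and IA2 lists do include "For HBeAg-positive participants: proportion of participants with HBeAg loss (undetectable HBeAg) and/or anti-HBe seroconversion", but that is secondary endpoint 12, not endpoint 7. Both lists refer back to Section 4.4.1, which already limits seroconversion to follow-up visits. Section 4.10.1 also combines IA1 with IA2. No separate defect remains there.
- **Little is at stake.** No hypothesis test or formal cohort comparison is planned, cohorts start at about 10 to 15 participants, and individual values are listed. This stands as to importance. It does not remove the defect: a listing can show that the first anti-HBe sample was at F1, but it cannot recover when an on-treatment event happened.

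**Conclusion.** The point holds in a limited form. As written, endpoint 7 calls for a seroconversion time that the anti-HBe data cannot supply for events during treatment. For treatment completers whose seroconversion occurs on treatment and persists, the recorded time is about Week 37 or 41 (3a), 45 (1a, 2a, 4a) or 49 (5a). It reflects treatment length, with artefactual gaps of 4 weeks (5a against 4a) and 8 or 12 weeks (5a against 3a).

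Those gaps assume attendance at F1 on schedule and a time origin of Day 1. They appear at full size only if all events behave this way. Early stoppers and events arising in follow-up would dilute them, by an amount the documents do not allow one to estimate.

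The importance is minor. The affected result is descriptive and exploratory, in HBeAg-positive participants only. A reader might infer harm to the primary endpoint or to the seroconversion proportion in endpoint 12. Neither follows: the primary endpoint does not use anti-HBe, and endpoint 12 is already confined to follow-up visits.

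**What to change.** For exploratory endpoint 7, summarize time to HBeAg loss on its own. Report anti-HBe seroconversion as the proportion at each follow-up visit, as endpoint 12 already does.

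If a seroconversion time is kept, report it as weeks after EOT to first detection in follow-up, or treat it as interval-censored between Screening and the first positive follow-up sample. In either case, do not compare it across cohorts.

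Because endpoint 7 stands in Table 1 of the SAP, record the change in Section 4.10. The IA1 and IA2 lists need nothing beyond following Section 4.4.1.

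The cost is SAP wording and some reprogramming of one summary; no new data are needed. What is given up is a time to seroconversion counted from Day 1, which cannot be interpreted for events during treatment.
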